- 6) Patients discontinuing study treatment for reasons other than disease progression will be reassessed at 3-month intervals to assess the time to treatment failure (progression / death). Follow-up until progression will be suspended in patients in whom a new cancer treatment has been started without prior documentation of progressive disease. Information on survival status may be captured by telephone if no follow-up visit is scheduled for other reasons.
- 7) If treatment was discontinued because of a drug-related adverse event (i.e., causality at least possibly related), the patient will be followed up as clinically indicated to assess and document the outcome.
- 8) Only required in women of child-bearing potential
- 9) Only a patient developing signs of cardiac failure during post-treatment follow-up will have LVEF and ECG evaluated; a left ventricular dysfunction of CTCAE grade 4 will be reported as an SAE.
- 10) Only anticancer treatments that a patient received during post treatment follow-up for survival will be recorded.
- 11) For tests performed by a laboratory not affiliated to study site (e.g. mid-cycle controls by the patient's home doctor) copies of the external laboratory reports will be provided to the sponsor and results recorded in the CRF.
- 12) A PK sub-study, including electrocardiographic evaluations on Day 1 and Day 2, will be conducted at selected investigational sites. Procedures are described in [APPENDIX 7](#)
- 13) Every effort should be made to start treatment within 4 days of randomization.
- 14) Specimens from FFPE fresh biopsies if FFPE archival tumor specimens are not available.
- 15) Except for Day 1 clinical laboratory tests
- 16) Recommended to be conducted also at end of Cycle 7 and 8 (i.e., before start of Cycle 8 and Cycle 9, respectively) for both arms. Results are to be captured on the eCRF if there is an abnormal finding.
- 17) Sparse PK sampling of AEZS-108 treated patients will be performed at all investigational sites, where feasible. Sparse PK sampling is expected in Cycle 1 or alternatively in a subsequent cycle of ongoing patients, within the following time windows:
 - sample #1: within 60 minutes before end of the 2-hour infusion (during 2nd half of the infusion period);
 - sample #2: between 30 and 60 minutes after the end of infusion (EOI);
 - sample #3: between 120 and 180 minutes after EOI;
 - sample #4 (optional): between 4 and 6 hours after EOI.

TABLE OF CONTENTS

Protocol Authorization.....	2

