7.1.7 Progression-Free Survival (PFS)

PFS is defined as the time elapsed from randomization to the date of documented progression or death, whichever comes first. For surviving patients without progression who begin alternative treatment, PFS will be censored at the last date of documented progression-free status prior to starting alternative treatment. Similarly, losses to follow up will be censored at the last date of documented progression-free status.

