8.6.1 Follow-up until progression

Whenever possible, a patient who has discontinued study treatment for other reason than progressive disease will be followed up at 3-monthly intervals until progression including the following assessments:

- **Clinical assessments** (including ECOG performance status, blood pressure, pulse)
- **Tumor imaging (CT or MRI):** evaluation of time-point response by comparison with target and non-target lesions at time of Best Response
- **Quality of Life:** questionnaires

Anticipated exceptions from follow-up will be “withdrawal of consent”, “lost to follow-up”, “patient moved”.

Follow-ups until progression will be suspended in patients in whom a new cancer treatment has been started without prior documentation of progressive disease. The start date of the new systemic therapy (or local therapy directed to lesions on which response assessment was based) will be documented.

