### **7.2.4 PFS: Definition**

PFS is defined as the number of days between randomization and the date of progression or death that occurred up to the end of study. PFS for patients who progress and then subsequently die will be the number of days between randomization and the date of progression is first observed.

Progression should be confirmed as specified. PFS data will be censored for subjects whose PFS status cannot be determined. The table below summarized rules of determining the dates of progression and censoring:

Situation	Date of Progression or Censoring	Outcome
No baseline tumor assessments	Randomization	Censored
Progression documented between scheduled visits	Date of the documented progression	Progressed
No progression	Date of last visit with adequate assessment	Censored
Treatment discontinuation for undocumented progression	Date of last visit with adequate assessment	Censored
Treatment discontinuation for toxicity or other reason	Date of last visit with adequate assessment	Censored
New anticancer treatment started	Date of last visit with adequate assessment	Censored
Death between adequate assessment visits	Date of death	Progressed
Death or progression after more than one missed visit	Date of last visit with adequate assessment	Censored

Once the dates of progression, survival, and censoring are derived, PFS will be calculated as follows:

For those who died or progressed up to the end of the study,

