### **7.2.6 PFS: Supportive and Sensitivity Analysis**

As a supportive analysis, PFS will be analyzed based on the modified ITT and PP populations. The same Cox models as defined for OS (see Section 7.1.3) will be made. In

addition, PFS will be analyzed in the subset of patients from MITT that have CR, PR or SD as best overall response.

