### 7.4 Adjustments for Multiplicity

One non-binding efficacy interim analysis is planned for this study. Lan-DeMets implementation of the O'Brien-Fleming alpha-spending function will be used to control

the overall Type I error rate at 0.05. The study has one primary efficacy endpoint; no p-value adjustment for multiple endpoints is required.

Two key secondary efficacy variables, PFS and ORR will also be analyzed for potential labeling claims. Hierarchical testing procedures will be used to control the Type I Error at the 0.05 level. Specifically, the superiority of the active treatment will be tested at a two-sided significance level of 0.05 for OS first, then for PFS, and then for ORR. The superiority claim for an efficacy outcome can be made only if all previous claims are successfully made.

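### No planned PFS analysis varies the censoring at new therapy or undocumented progression, so switching that is both progression-related and unequal between arms would go undetected

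*Protocol*

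**What the plan says.** **Follow-up.** Protocol 8.6.1 follows patients who stop treatment without progression every 3 months, with one exception: "Follow-ups until progression will be suspended in patients in whom a new cancer treatment has been started without prior documentation of progressive disease". Flow-chart footnote 6 and SAP Appendix A repeat this.

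**Censoring.** Protocol 7.1.7 states: "For surviving patients without progression who begin alternative treatment, PFS will be censored at the last date of documented progression-free status". In the SAP 7.2.4 table, the rows "New anticancer treatment started" and "Treatment discontinuation for undocumented progression" both lead to censoring at the last visit with an adequate assessment.

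**Supportive PFS analyses.** SAP 7.2.6 says: "As a supportive analysis, PFS will be analyzed based on the modified ITT and PP populations". It adds: "The same Cox models as defined for OS (see Section 7.1.3) will be made", and then a subset of MITT patients whose best response is CR, PR or SD. Tables 14.2.13 to 14.2.17.2 and Figures 14.2.5 to 14.2.8 in Appendix E list the same set. The only sensitivity analysis keyed to new therapy is in SAP 7.1.3. It concerns OS, and it adds censoring.

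**Role of PFS.** SAP 7.4 says: "Two key secondary efficacy variables, PFS and ORR will also be analyzed for potential labeling claims". Testing runs in the order OS, PFS, ORR.

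**The concern.** A patient who is deteriorating and is moved to another therapy before RECIST progression is on file leaves the PFS risk set at her last clean scan, shortly before her event would have been recorded. A patient who stops for progression that was never documented is treated the same way. If such patients are closer to progression than those who remain, the censoring is informative.

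The log-rank comparison survives this if it happens equally in both arms. Here it need not. The trial is open-label, Protocol 6.4 leaves the choice and timing of further therapy to the investigator, and Protocol 5.3 lists deterioration together with progressive disease as a reason for withdrawal. The arm with more such switching would show the better PFS.

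The planned supportive analyses change the population or the covariates and keep the same censoring rule. They would therefore agree with the primary analysis whether or not it is biased.

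**Working it through.** **The plan's own figures.** The plan gives no PFS event count, PFS power or switching rate to reproduce. Its only sizing figure is 384 deaths for OS. With HR 9/12 = 0.75, the Schoenfeld formula gives 4 × (1.960 + 0.842)² / (ln 0.75)² ≈ 380, and Freedman's gives 385. That figure reproduces but has no bearing on this point.

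**Inputs from the documents.** Scans every 9 weeks on treatment (Protocol 7.1). About 250 patients per arm, 24 months' accrual and 12 months' further follow-up (Protocol synopsis, SAP 7.5). Log-rank test at two-sided 0.05 (SAP 7.2.5).

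**Assumptions.** Exponential PFS with median 4 months in both arms (true HR 1.00). A fraction f of each arm switches on clinical deterioration at the time of true progression. In a share c of those switchers, an off-schedule or end-of-treatment scan documents the progression. The remainder are censored at the previous scan.

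**Approximation.** The hazard of a documented event is reduced by the factor 1 − f(1 − c), so the apparent HR ≈ [1 − f_A(1 − c)] / [1 − f_B(1 − c)]. For 20% v 10%:
- c = 0: 0.80 / 0.90 = 0.889
- c = 0.5: 0.90 / 0.95 = 0.947
- c = 0.8: 0.96 / 0.98 = 0.980

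**Simulation.** This adds the scan grid and the log-rank test, with 2000 or more replicates. False superiority means a one-sided result in favour of the arm with more switching; its nominal value is 2.5%.

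| Switching | Capture c | Apparent HR | False superiority |
|---|---|---|---|
| 20% v 10% | 0 | 0.89 | 17-18% |
| 20% v 10% | 50% | 0.96-0.97 | 3-6% |
| 20% v 10% | 80% | about 1.00 | near nominal |
| 15% v 10% | 0 | 0.95 | 7% |
| 25% v 10% | 0 | 0.83 | 33-36% |
| 25% v 10% | 50% | 0.94 | 9% |
| 25% v 10% | 80% | 0.99 | 3% |

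With capture, the simulated HR lies a little nearer 1 than the approximation, because a captured progression is dated at an off-schedule scan, earlier than the next 9-week scan. The zero-capture results barely change for PFS medians of 3 to 7 months.

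**Controls.**
- Equal informative switching (10% v 10%): HR 1.00.
- Unequal switching unrelated to prognosis: HR 1.00, two-sided rejection about 5%.
- Arms reversed (10% v 20%): 0.90 / 0.80 = 1.125, simulated 1.12.
- Switch counted as an event, 20% v 10%: HR 1.04, false superiority about 1%. When captures are few, this rule and the planned one fall on opposite sides of the true value.

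**The case against.** The strongest reply is that the protocol already works against this problem. Protocol section 4 and SAP 2.2 call for earlier reassessment when progression is suspected. Protocol 8.5 requires CT or MRI for any patient going off treatment, 3 to 5 weeks after the last dose. Protocol 7.1.5.3 asks for every effort to document objective progression after symptomatic deterioration. SAP 7.2.4 counts progression found between scheduled visits on its own date. This stands, and it is why zero capture is a worst case. A reader might infer from 8.6.1 that progression in a switcher is never observed. The documents do not support that: it is lost only if these scans are missed, fall short of PD, or come after the new therapy has started.

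Second, a reader might take 17-18% as the chance of a false PFS claim. It is not. Under SAP 7.4 a PFS claim requires OS to succeed first, and the PFS rule does not touch OS.

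Third, a reader might infer that any imbalance in switching biases PFS, or that the bias favours AEZS-108. The controls show that switching must also be tied to impending progression. The direction depends on which arm switches more, and the documents do not say.

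Fourth, an imbalance would be partly visible in the planned summaries of subsequent therapy (SAP 6.5) and reasons for discontinuation (SAP 5.1). That is true, but those tables do not show what the imbalance does to the PFS estimate.

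**Conclusion.** The gap is real and limited. The censoring rule is stated in advance and consistently, but no planned PFS output tests the assumption behind it, although PFS is a key secondary endpoint intended for labeling.

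The possible distortion runs from none to material. At an assumed 20% v 10%, it runs from about HR 1.00 with 80% capture to about HR 0.89 with none. These figures rest on assumed switching shares, an assumed capture rate, an exponential PFS model, and switching that occurs at true progression. The documents supply none of these, so the figures show what could happen and do not forecast it. The primary endpoint is unaffected. This is a cheap improvement to a gated secondary analysis and does not call the design into question.

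**What to change.** Add to SAP 7.2.6 and Appendix E one ITT PFS sensitivity analysis in which the following also count as events, on the date they occur:
1. start of new anticancer therapy before documented progression;
2. discontinuation for lack of efficacy, deterioration or undocumented progression with no RECIST PD on file. The last condition is needed because Protocol 5.3 places progression and deterioration in one category.

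Report it beside the primary PFS analysis, with the number of patients censored for each reason by arm.

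**Cost.** One table and one Kaplan-Meier figure. Protocol 8.6.1 already records the start date of new therapy, and 8.5 the reason for discontinuation.

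**Downside.** The analysis counts unblinded investigator decisions as events and slightly over-corrects against the arm with more switching (HR 1.04 at 20% v 10%). It should serve as a sensitivity analysis only.

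Collecting progression dates from routine-care scans after the switch is not recommended. Without a common schedule and under a different drug, ascertainment would be uneven and hard to interpret.

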8.6.2 Follow-up for survival

For patients going off study, survival information will be collected at 3-month intervals, telephone contact is acceptable.

9 STATISTICAL CONSIDERATIONS

The sections of the Statistical Considerations describe the statistical methods to be used to analyze the efficacy and safety. These methods may be revised and updated due to reasons such as regulatory requirements or need for further clarifications. The final analysis plan will be documented in a formal statistical analysis plan (SAP) that must be finalized before database lock. The SAP will include details on how variables will be derived, how missing data will be handled, and how censoring procedures will be applied to time to event related variables as well as the details on statistical methods to be used for safety and efficacy analyses. The final clinical study report will discuss deviations from the SAP, if any.

Unless otherwise stated, all analyses will be performed using SAS Version 9 and all hypothesis tests will be conducted at a two-sided significance level of 0.05.

Summary tabulations will display the number of observations, mean, standard deviation, median, minimum, maximum, and appropriate percentiles for continuous variables, and the number and percentage by category for categorical data. Summaries will present data by treatment arm and overall, if appropriate. The data listings will include all available efficacy and safety data.

9.1 Analysis populations

The following populations will be used for statistical analysis.

9.1.1 Intent-to-treat population

The Intent-to-Treat (ITT) population will consist of all randomized patients. Analyses of this population will assign patients the treatment they were scheduled to receive, regardless of any errors of dosing or dose modifications.

9.1.2 Safety population

The safety population will include all randomized patients who received at least one dose of study treatment. In the safety analyses, patients will be included in the treatment arm that they have actually received.

9.1.3 Per protocol population

The Per-Protocol (PP) population will include all randomized patients without major protocol deviations. What constitutes a major protocol deviation will be determined and documented prior to database lock. Protocol deviations will also be presented in the clinical study report.

9.2 Demographic and baseline characteristics

The two treatment arms will be assessed descriptively for comparability of demographic and baseline characteristics. Data to be evaluated will include at least age, race, and components of disease severity assessment.

9.3 Treatments and medications

9.3.1 Prior treatment for endometrial cancer

Use of prior treatment for endometrial cancer will be presented as frequency counts and percentages. Descriptive statistics for the number of prior lines of therapy will also be presented. Prior chemotherapy will be coded using the World Health Organization (WHO) dictionary and summarized by treatment arms for the safety population.

9.3.2 Prior and concomitant medications

All medications recorded on the CRFs will be coded using the WHO dictionary. Prior and concomitant medications will be summarized by treatment arm in the safety population by anatomical therapeutic chemical (ATC) class level 4 and WHO Drug base substance preferred name.

Prior medications are defined as medications with stop dates occurring before the date of first administration of study treatment. Concomitant medications are defined as medications with start dates occurring on or after the date of first administration of study treatment but no later than 30 days after the last administration of study treatment. Medications with start and stop dates that overlap the date of first administration of study drugs will be summarized as both prior and concomitant medications.

9.3.3 Study treatment

Study treatment exposure (e.g., number of treatment cycles, total drug exposed) will be summarized by treatment arm in the ITT and safety populations.

Treatment modifications will be summarized by treatment arm in the ITT and safety populations for each of the study treatments separately. The number and percentage of patients with doses delayed (withheld) and doses reduced, and reasons for these dose changes will be summarized by treatment cycle.

A summary of the number and percentage of patients receiving subsequent alternative anticancer therapy after discontinuation of study treatment will be presented by treatment arm in the ITT population.

9.4 Primary efficacy outcome

9.4.1 Definition

The primary efficacy outcome is overall survival (OS). Overall survival will be defined as the days between randomization and the date of documented death for any cause. For patients whose survival status cannot be determined, their OS data will be censored at the last documented date that the patient is confirmed to be alive.

9.4.2 Primary analysis

The primary efficacy analysis will be performed using the ITT population. The final analysis, which is event-based, will be conducted after approximately 384 randomized patients have died. In the primary analysis, a log-rank test with an overall two-sided Type I error rate of 0.05 after taking the interim analyses into account will be used to compare OS between the two treatment arms via a SAS lifetest procedure. Kaplan-Meier estimates will be used to calculate median OS and the 95 % confidence interval of the median OS. The proportion of patients alive at six and 12 months (from randomization date) and the 95 % confidence intervals for these estimated proportions, if appropriate, will be presented.

A Cox model with treatment effects will be used to estimate the hazard ratio and perform hypothesis testing. The estimated hazard ratio and the 95 % confidence interval of the hazard ratio will be presented.

9.4.3 Sensitivity analyses

The following sensitivity OS analyses will be performed:

1. Patients who changed treatment will be censored at the day the patient received the new treatment;
2. PP analysis.

Additional sensitivity analyses may be performed as appropriate.

9.4.4 Subgroup analyses

OS will also be analyzed for the following subgroups:

1. Age (≤ 64 and > 64 years of age)
2. Staging (FIGO stage III or IV)

Additional subgroup analyses may be performed if appropriate. In particular, if the strength of the LHRH receptor expression can be classified, subgroup analyses based on the strength of LHRH receptor expression will be performed.

9.4.5 Exploratory analyses

Exploratory analyses to evaluate potential risks/benefits factors may also be performed.

9.5 Secondary efficacy outcomes

9.5.1 Progression free survival (PFS)

Progression-free survival will be defined as the days between randomization and the date of documented progression or death for any cause. Criteria for disease progression can be found in [Section 7.1.7](#).

For patients whose progression status cannot be determined, their PFS data will be censored at the last adequate progression assessment date that the patient is confirmed to have no progression.

Hypothesis testing between the two treatment arms will be performed using a log-rank test.

For each treatment arm, the median time to progression will be estimated using the Kaplan-Meier method and the 95 % confidence interval of the median will be reported.

9.5.2 Overall response rate (ORR) and clinical benefit

The ORR for each treatment arm will be estimated as the proportion of responders, defined as a patient whose best overall response is PR or better during the treatment period. All responses must be confirmed at least 4 weeks after the initial response is seen. Tumor assessments will occur every 3 cycles (± 7 days) during ongoing treatment then every 3 months (± 7 days) thereafter while the patient is on study. The last assessment will occur either when progression is confirmed or when approximately 384 randomized patients have died

Hypothesis testing between the two treatment arms will be performed using a Mantel-Haenszel test. The odds ratio and 95 % confidence interval of the odds ratio will be presented.

Clinical benefit is defined as having stable disease or better lasting for at least 9 weeks. Clinical benefit rate will be analyzed using the same methods for the ORR analyses.

9.5.3 Quality of life

Change from baseline in Quality of life will be analyzed via an ANOVA model with treatment effect and baseline quality of life score. The treatment effect and treatment difference will be estimated and the 95 % confidence interval of the estimates will be presented.

9.6 Safety analysis

Safety evaluations will be based on the incidence, intensity, and type of adverse events, as well as on clinically significant changes in the patient's physical examination, vital signs, and clinical laboratory results. Safety analyses will be performed using the safety population. Safety variables will be tabulated and presented according to the treatment the patient actually received. Exposure to study treatment and reasons for discontinuation of study treatment will also be tabulated.

